## 12. SAP- Statistical Analysis Plan

- to prove the homogeneity of the compared groups, analysis of the baseline parameters was done
- to show the potential differences between people with pre-DM and healthy people the comparison of the baseline parameters was done
- to follow the metformin intake by the patients, the metformin concentration with its change during the therapy was done
- for the analysis of the impact of the metformin dosage on the concentration of the compounds related to the production of the NO the difference of these compounds between two groups was done
- as an extra analysis, the correlations of the serum drug concentration with BMI and body mass, after 6 and 15 weeks of the treatment was done, while research was ongoing

[figure not shown]
The Statistica 13 program was used with cut-off point for statistical significance (P) at 0.05.

The normality of the distribution of the examined quantitative variables was checked using the Shapiro-Wilk test. In order to determine the significance, statistical tests were used in accordance with the distribution of variables and the nature of the data (Student t test, Welch test, Mann-Whitney test, chi – square test, the Wilcoxon signed-rank test, Kruskal – Wallis test, Friedman test, F test). To determine the correlation the Spearman's rank-order correlation and the Pearson correlation was used.

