### **Material and Methods:**

#### *Population and groups*

The treatment-naïve patients (regarding to hypoglycemic drugs) with new-diagnosed pre-DM were recruited from Diabetes Centre between October 2017 and December 2018.

Inclusion criteria for the patients:

- Pre-diabetes based on FG (fasting glucose) and / or OGTT (oral glucose tolerance test) according to the local (similar to EASD- European Association for the Study of Diabetes) criteria
- Age 40-65 yo
- Any gender, profession, place of residence
- Negative history for diabetes
- No hypoglycemic drugs in the past
- Negative history for cardio-vascular diseases
- Written consent to participate in the study

Criteria for exclusion for the patients:

- Age <40 or >65 years
- History of diabetes –from patients, patients family and/or medical records if available
- FG>125 mg% (6.9mmol/L) and or glucose after 2 hours in OGTT >199mg% (11mmol/L)
- History of treatment with any hypoglycemic drug
- History of cardio-vascular disease
- Contraindications to the use metformin according to the Product Characteristics
- Known gastro-intestinal disease which could be potentially responsible for metformin intolerance (eg IBD- irritable bowel disease, GERD- gastro-esophageal reflux disease)

- Known potential difficulties in collaboration with patients (dementia, mental disorders, distance from patients residence if considered as potentially problematic)
- No consent to participate in the study
- Patient participation in another study

Inclusion criteria for \* healthy volunteers:

- Age 40-65 yo
- Any gender, profession, place of residence
- Negative history for diabetes, pre-diabetes and FG<100 mg% (5.6 mmol/L)
- No hypoglycemic drugs in the past
- Negative history for cardio-vascular diseases
- Written consent to participate in the study

***Methods: definitions, information collected, lab-tests performed, treatment scheme, lab-tests technique, statistical analysis***

1. Pre-diabetes diagnosis definitions:

IFG (impaired fasting glycaemia): FG (fasting glucose): 100-125 mg% (5.6- 6.9 mmol/L);

IGT (impaired glucose tolerance): glucose 140-199 mg% (7.8- 11.0 mmol/L) after 2 hours of 75 glucose solution taken

2. Negative history for cardio-vascular diseases definitions:

Patients without ischemic heart disease and/or stroke and/or PAOD (peripheral arterial occlusive disease) in a history

3. Demographic information collected: age, sex

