4. Baseline parameters collected: weight, height, BMI (body mass index), information about fatty liver (based on the available ultrasonography organs' description), family history for DM (YES/NO), hypertension (YES/NO), active nicotinism (YES/NO); and biochemical: FPG, lipids profile, creatinine, AlaT (alanine transaminase), creatinine, HbA1c (glycated hemoglobin) if available.

5. Before the first dose of the metformin and after: 6, 12, 15 weeks of the treatment, the blood samples were collected for the assessment of the:

a. concentration of the metformin

b. concentration of the compounds related to the production of the NO: L-arginine, L-citrulline, ADMA – asymmetric dimethylarginine, DMA – dimethylamine, SDMA – symmetric dimethylarginine, ornithine

\* For healthy volunteers only once concentration for the compounds related to the production of the NO was assessed and no blood samples for metformin concentration were taken.

The admissible delay in taking blood for lab-testing was set at 4 days. The blood samples were taken randomly (no hours or gaps between metformin taking were defined).

6. Patients with pre-DM were treated 3 weeks with an increasing dose of the immediate-release (regular form) metformin to 3 x 500 mg, and then randomly assigned to:

group A – continuation of a dose of 3 x 500 mg or

group B – increase dose to: 3 x 1000 mg (also by titration); after 12 weeks this group returned to the dose 3 x 500 mg for the next 3 weeks

7. If potential side effects appeared in group B, the patients could take a lower dose (3 x 500 mg if well-tolerated) and thus change to group A.

8. If the smallest dosage (3 x 500mg) was not tolerated the patient was excluded from the study.

9. During titration period (by phone) and blood collection visits (personally), patients were asked about the compliance and drug's tolerance. The patients were also encouraged to contact in any case of the problem with metformin tolerance.

10. The technique used to assess concentration of the metformin in serum and the wider panel of L-arginine/NO pathway metabolites: LC-MS/MS (liquid chromatography-mass spectrometry).

11. Safety outcomes: Adverse events were reported at each clinic visit and revised via telephone contact during treatment period.

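### The SAP's first bullet asks the baseline analysis to prove the groups homogeneous, which difference tests at P = 0.05 cannot do

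*Combined protocol and SAP*

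**What the plan says.** Section 12 (SAP) opens its list of analyses with "to prove the homogeneity of the compared groups, analysis of the baseline parameters was done". The comparison with healthy people has its own bullet, so the compared groups here are most naturally A and B, which Methods item 6 says were formed by random assignment.

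The bullet names no method. For the analyses as a whole, the section says "In order to determine the significance, statistical tests were used in accordance with the distribution of variables and the nature of the data", lists the tests (t, Welch, Mann-Whitney, chi-square and others), and sets one "cut-off point for statistical significance (P) at 0.05". Its text gives no equivalence margin, standardised difference or confidence interval.

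The variables appear in two places: item 3 ("Demographic information collected: age, sex") and item 4, which begins "Baseline parameters collected: weight, height, BMI (body mass index), information about fatty liver" and continues with history items and routine biochemistry. The six NO-pathway compounds measured before the first dose are in item 5.

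The dose analysis (fourth bullet of section 12) is a difference in these compounds between the two groups, with no baseline adjustment named. Item 7 lets a group B patient with side effects drop to the lower dose and be counted in group A. No analysis set is defined.

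**The concern.** A test of difference can reject equality or fail to reject it; failing to reject does not establish equality. Nothing in the SAP's text can deliver the proof that the first bullet promises.

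What is at stake is interpretation. The dose comparison names no adjustment, so a report that calls the groups proven alike invites the reader to discount baseline imbalance as a contributor to the A versus B difference. A sizeable imbalance can sit below the cut-off and be reported as homogeneity. With this many variables, a harmless chance difference can equally be flagged as if it meant something. If the groups are formed after patients have switched, the same wording could hide selection.

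**Working it through.** The plan has no figure of its own to reproduce: it states no sample size, SD or effect size, only the 0.05 cut-off.

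**Inputs**
- Cut-off 0.05 (section 12). Sidedness is not stated; two-sided is assumed.
- Allocation is random (item 6). The ratio is not stated; 1:1 is assumed.
- n per group is not stated; 15 to 40 is assumed, with 100 for contrast.
- Variables from items 3 and 4: age, sex, weight, height, BMI, fatty liver, family history, hypertension, smoking, FPG, lipids, creatinine, AlaT, HbA1c. That is 14 with lipids counted once, or 17 if the lipid profile is taken as four values (assumption).

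**Step 1: largest observed imbalance that stays non-significant.** For a two-sample t test, in SD units, this is t(0.975, 2n−2) × √(2/n).

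| n per group | t | √(2/n) | limit (SD) |
|---|---|---|---|
| 15 | 2.048 | 0.365 | 0.75 |
| 20 | 2.024 | 0.316 | 0.64 |
| 30 | 2.002 | 0.258 | 0.52 |
| 40 | 1.991 | 0.224 | 0.45 |
| 100 | 1.972 | 0.141 | 0.28 |

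Yes/no factors behave in the same way. At 20 per group, 6/20 against 12/20 (30% against 60%) gives an uncorrected chi-square of 40 × (6×8 − 14×12)² / (18 × 22 × 20 × 20) = 3.64, P = 0.057.

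**Step 2: what such an imbalance does to the dose estimate.** An imbalance of d SD in a variable with within-group correlation r to the outcome moves the unadjusted A versus B difference by about r × d outcome SDs. At n = 20, with r assumed to be 0.5 or 0.7, this is 0.5 × 0.64 = 0.32 or 0.7 × 0.64 = 0.45 SD. This is the edge case: in randomised groups of 20, an imbalance of 0.64 SD or more on a given variable occurs 5% of the time.

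**Step 3: chance flags in groups as randomised.** With k independent tests, the probability of at least one P < 0.05 is 1 − 0.95^k.
- k = 14: 1 − 0.488 = 51%
- k = 17: 1 − 0.418 = 58%
- Without age and sex, k = 12 or 15: 46% or 54%
- With the six NO compounds added, k = 20 or 23: 64% or 69%

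BMI is computed from weight and height, and lipid values are correlated, so these figures are approximate.

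**Step 4: groups after switching.** Steps 2 and 3 treat every imbalance as chance. If group B patients with side effects are counted in A, the groups differ partly by tolerance, and a true baseline difference becomes possible. The limits in Step 1 then show how much observed selection a non-significant test would let through (approximate, since the group sizes would no longer be equal).

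**The case against.** The case on the other side has real content.

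- **Randomisation is the main protection.** It removes systematic differences between A and B as randomised, and the standard error of the unadjusted comparison already allows for chance imbalance (√(2/20) = 0.32 SD at 20 per group). This stands. The homogeneity bullet is not the only thing supporting the dose comparison, and that comparison is not invalid because of it.
- **The method is inferred.** The bullet names no test. This also stands, but significance tests are the only comparison methods that the section's text offers.
- **Size depends on an unstated n.** True. At 100 per group only about 0.28 SD stays hidden. The faulty inference does not depend on n.
- **Describing instead of testing does not move the estimate.** Correct, which is why the fix has a second part.

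A reader might also infer four stronger things that the documents do not support.

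1. That a 0.5 SD imbalance is missed 74% to 40% of the time at 15 to 40 per group. Those are type II error rates for a true difference, and randomisation makes the true difference zero. They could bear only on groups formed after switching, where the size of any selection is unknown.
2. That an undetected imbalance passes in full into the dose estimate. It passes in proportion to its correlation with the outcome.
3. That the six NO compounds were left out of the homogeneity check. Item 4 does not list them, but the second bullet uses the same term for the comparison with healthy people, whose only stated assessment in item 5 is those compounds. The term is undefined; omission is one reading.
4. That baseline P values decide whether to adjust. Nothing in the plan says so.

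**Conclusion.** The point holds: the conclusion that the first bullet sets out to draw cannot be drawn with the methods given. The exact statement is that a non-significant test does not prove homogeneity; it is not that the test carries no information, or that the groups are unbalanced.

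The size rests on the assumed n, 1:1 allocation and two-sided testing: hidden imbalances of up to 0.75 SD (15 per group) to 0.45 SD (40 per group), falling with larger groups. The 51% to 58% chance-flag probability applies only to groups as randomised and assumes independent tests. For groups compared after switching, the concern is instead that real selection may be certified away.

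The harm is false assurance in the report and a chance imbalance left unaddressed in the dose comparison. It warrants a change in the plan but does not overturn the comparison of randomised groups.

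**What to change.** Replace the first bullet with wording such as: *Baseline parameters and the six pre-dose NO compounds are described by randomised group, with standardised differences. No baseline significance tests are made and no conclusion of homogeneity is drawn.* This also settles whether the compounds belong in the table.

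Add to the fourth bullet: *Each NO compound is compared between the groups as randomised, adjusted for its own pre-dose value (for example by ANCOVA), whatever baseline balance is observed.* The pre-dose sample precedes the first dose and therefore randomisation, so it is a legitimate covariate. This second change is the one that deals with imbalance in the dose estimate.

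The cost is one re-laid baseline table and one model per compound, from data already collected; what is given up is the claim of proven homogeneity. Because the SAP is written in the past tense, an adjusted analysis added now should be reported as specified after data collection.

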### **Aim:**

The study evaluated the effect of different doses of metformin on the intermediates of NO (nitric oxide) biosynthesis in people with pre-DM (pre-diabetes).

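### Minor, cheap improvement: the pre-DM versus healthy comparison is non-randomised and no adjusted analysis is named, so report an age- and sex-adjusted estimate beside the unadjusted one; undiagnosed IGT among volunteers is not excluded

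*Combined protocol and SAP*

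**What the plan says.** The SAP (item 12) lists this among its analyses: "to show the potential differences between people with pre-DM and healthy people the comparison of the baseline parameters was done". It gives no outcome list, model or covariates for it. On method it says that "statistical tests were used in accordance with the distribution of variables and the nature of the data (Student t test, Welch test, Mann-Whitney test" and further tests were used, ending with an F test whose purpose is not explained. For association it names Spearman and Pearson correlation.

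The two groups enter by different glycaemic routes (Population and groups). Patients qualify by "Pre-diabetes based on FG (fasting glucose) and / or OGTT (oral glucose tolerance test", and Methods item 1 has "IGT (impaired glucose tolerance): glucose 140-199 mg% (7.8- 11.0 mmol/L) after 2 hours" as one form of pre-diabetes. Volunteers need "Negative history for diabetes, pre-diabetes and FG<100 mg% (5.6 mmol/L", and no OGTT is asked of them. Volunteers must also be aged 40-65, have no cardiovascular disease history and have taken no glucose-lowering drugs. The patient criteria set the same limits.

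On data, Methods item 3 has "Demographic information collected: age, sex", without saying whether this covers volunteers. Methods item 5 notes: "For healthy volunteers only once concentration for the compounds related to the production of the NO was assessed".

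The Aim is a different question: "The study evaluated the effect of different doses of metformin on the intermediates of NO (nitric oxide) biosynthesis in people with pre-DM".

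**The concern.** Group membership here is not assigned at random, so patients and volunteers may differ in age and sex as well as glycaemia. A t, Welch or Mann-Whitney test describes the two groups validly, but it cannot say how much of a difference in, say, ADMA belongs to pre-diabetes and how much to an older or more male group. That error can go either way.

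The second issue is classification. A person with fasting glucose below 100 mg% and a 2-hour value of 140-199 mg% has pre-diabetes by the protocol's own definition. If never tested, that person can enter as a healthy volunteer. If such volunteers have compound levels between those of the other volunteers and the patients, or equal to the patients', the observed difference shrinks.

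What is at stake is how the pre-DM versus healthy difference is read, and nothing more.

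**Working it through.** **1. Text check.** Randomisation (Methods item 6) applies only to groups A and B among the patients. The methods visible in item 12 are Student t, Welch, Mann-Whitney, chi-square, Wilcoxon signed-rank, Kruskal-Wallis, Friedman and F tests, with two bivariate correlations. No regression, ANCOVA, matching or weighting appears. None of the volunteer criteria other than known history can detect isolated IGT.

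**2. What can be computed.** The documents give no volunteer number, age or sex mix, IGT share, effect size or SD, so there is no figure of the plan's own to reproduce. Everything below is illustrative. The only input taken from the documents is the 40-65 age limit.

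**3. Dilution by undetected IGT.** Let Δ be the true difference between patients and truly normal volunteers, p the share of volunteers with undetected IGT, and k the fraction of Δ that they carry. The observed difference is Δ(1 − pk).
- p = 0.05, k = 0.5: 1 − 0.025 = 0.975
- p = 0.20, k = 1: 1 − 0.20 = 0.80

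**4. Age.** As a reference scale, ages spread evenly over 40-65 have SD 25/√12 = 7.22 years. Assume a mean gap of 2-5 years and a correlation r of 0.1-0.3 between age and a compound. The shift in the unadjusted difference is (gap/SD) × r.
- 2/7.22 = 0.277; × 0.1 = 0.028 SD
- 5/7.22 = 0.693; × 0.3 = 0.208 SD

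**5. Sex.** Assume a gap of 10-30 percentage points and a sex difference of 0.2-0.5 SD.
- 0.10 × 0.2 = 0.02 SD
- 0.30 × 0.5 = 0.15 SD

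**6. Price of adjusting.** If age and sex explain nothing in the outcome, the standard error grows by the factor 1/√(1 − R²), where R² = D²/(D² + 1/(π(1 − π))). D² is the sum of squared standardised gaps and π the share of patients. The factor simplifies to √(1 + D²π(1 − π)).
- 2 years and 55% versus 45%: D² = 0.277² + 0.10²/(0.55 × 0.45) = 0.117. The factor is 1.013 at 2:1 and 1.015 at 1:1.
- 5 years and 65% versus 35%: D² = 0.693² + 0.30²/(0.65 × 0.35) = 0.876. The factor is 1.093 at 2:1 and 1.104 at 1:1.

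**7. Simulation at the upper end.** 10,000 runs, 50 patients and 25 volunteers (assumed), true adjusted difference 0, gaps of 5 years and 30 points.

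| Setting | Unadjusted mean difference | Adjusted mean difference | Mean SE, unadjusted | Mean SE, adjusted |
|---|---|---|---|---|
| r = 0.3, sex effect 0.5 SD | 0.357 SD | −0.001 SD | 0.244 | 0.251 |
| Age and sex unrelated to outcome | about 0 | about 0 | 0.244 | 0.272 |

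The first row agrees with 0.208 + 0.15 = 0.358. In the second row the standard error rises by 11%, slightly above the analytic 9.3% at 2:1. Hence the quoted cost of about 1-11%.

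**The case against.** The strongest reply is that the comparison is descriptive. The SAP sets out to show potential differences. No text attributes a difference to pre-diabetes independently of age or sex, and the contrast lies outside the Aim. For description alone, an unadjusted result with a clear label is enough. This stands: adjustment is an improvement, not a requirement.

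Four further points have weight.
- **Outcome.** Methods item 4 uses the term baseline parameters for anthropometric and routine laboratory items, while the NO compounds come in item 5. That the compounds are compared with volunteers is an inference. It is a reasonable one, because no other listed analysis would use the volunteers' sample.
- **Incomplete text.** A figure is missing from item 12 and the F test is unexplained, so only the visible text can be said to lack an adjusted model.
- **Homogeneity check.** Item 12 also plans a baseline check of the compared groups. If it includes volunteers, it would display an age or sex imbalance, though it would not remove it from the difference.
- **Magnitudes.** The sizes rest on assumptions. Two groups both spread evenly over 40-65 would share a mean of 52.5 years and show no gap, so 7.22 is a scale for the gap and not a model of both groups.

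A reader might infer stronger claims that the documents do not support. One is that healthy means nothing beyond a fasting glucose and no known pre-diabetes. The age, diabetes, drug and cardiovascular criteria contradict that. Another is that the 5% test has an inflated false-positive rate. It remains a valid test of whether the groups differ, and with no sample sizes or imbalances given, no error rate for a claim about pre-diabetes can be derived.

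**Conclusion.** The point holds as a minor one. The comparison is non-randomised, the visible text names no adjusted analysis, and volunteers are not stated to have had an OGTT. A difference in the NO compounds would therefore mix pre-diabetes with any age or sex imbalance, and undiagnosed isolated IGT among volunteers could dilute it.

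The actual size of either bias cannot be determined from the documents. The illustrative ranges run from negligible to moderate: a combined shift of at most about 0.36 SD with age and sex both at their upper assumed values, and a loss of 2.5-20% from dilution. The direction of the dilution assumes that volunteers with IGT lie between the other volunteers and the patients, or level with the patients.

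It would be wrong to conclude that the metformin dose findings are compromised. The volunteers play no part in the randomised A versus B comparison.

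**What to change.** For each of the six NO compounds before treatment, report two pre-DM versus volunteer differences, each with a 95% CI: the unadjusted one, and one from a linear regression on group, age and sex. Transform the outcome if the residuals require it. Label the analysis exploratory, and label the adjusted model post hoc if the data have already been analysed. If sex was not recorded for volunteers, adjust for age alone; age must be known, because it is an entry criterion.

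Keep BMI and hypertension out of this model, since they may be part of the pre-DM phenotype. They belong at most in an optional sensitivity analysis, if recorded for volunteers.

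Read the result as a difference between patients and volunteers with normal fasting glucose and no known pre-diabetes. Adjustment does not remove undetected IGT.

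The cost is SAP wording and one regression per compound, with no new test or participant. The downside is a standard error about 1-11% larger, on the assumed imbalances, if age and sex do not predict the outcome. Where they do predict it, part of that is recovered (0.244 to 0.251 in the simulation, about 3%).

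### The readable SAP names no baseline-adjusted comparison of groups A and B, although all six compounds are measured before the first dose; ANCOVA on that value would be more precise unless the correlation is low

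*Combined protocol and SAP*

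**What the plan says.** The SAP (section 12) covers the effect of dose on the nitric oxide compounds in one line: "the difference of these compounds between two groups was done". It gives no time point, does not say whether follow-up values or changes are compared, and names no covariate or model.

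The tests for quantitative data include "Student t test, Welch test, Mann-Whitney test" and Kruskal-Wallis, none of which takes a covariate. Wilcoxon signed-rank and Friedman are also listed, but they work within patients and give no contrast between A and B. The list ends with "Friedman test, F test", and the F test is not explained. Change over time is mentioned for the drug level only: "the metformin concentration with its change during the therapy was done". Baseline parameters are used to check that the groups are alike and to compare patients with healthy volunteers, not for adjustment.

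The baseline values exist. Methods item 5 states: "Before the first dose of the metformin and after: 6, 12, 15 weeks of the treatment, the blood samples were collected". The flow chart also shows all six compounds at the initial visit. Under Methods item 6, patients first take metformin for 3 weeks "and then randomly assigned to" group A or B.

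**The concern.** The pre-dose concentration is usually among the best available predictors of a later concentration in the same patient. If the A versus B comparison ignores it, stable differences between patients stay in the error term and the confidence interval for the dose effect is wider than it need be. If the comparison uses simple change scores instead, the baseline is used inefficiently. The dose comparison is the trial's stated aim, so avoidable imprecision falls on the main result.

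Only precision is at stake here. Methods item 7 lets group B patients who step down move to group A, and item 8 removes patients who cannot tolerate the lower dose. The SAP does not say that groups are compared as randomised. If they are not, bias is possible, and baseline adjustment does not remove it.

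**Working it through.** **Inputs.** From the documents: two randomised groups; significance level 0.05 (two-sided is assumed); each compound measured before the first dose and at weeks 6, 12 and 15. The plan has no sample size, SD, effect size or correlation, so there is no figure of its own to reproduce. Assumed: correlation ρ between the pre-dose and week-12 values of 0 to 0.7; n = 10, 25 or 50 per arm; true difference 0.5 SD; equal variances and a linear relation on the log scale.

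**Is the covariate valid?** Randomisation follows a 3-week run-in (Methods item 6) or a control visit on treatment (flow chart). On either reading the pre-dose sample comes first, so treatment assignment cannot have affected it.

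**Variance of the A−B difference** (t test on week-12 values = 1):

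- ANCOVA: 1 − ρ² = 0.91, 0.75, 0.51 at ρ = 0.3, 0.5, 0.7, which are cuts of 9%, 25% and 49%.
- Cost of estimating the slope: multiply by (2n − 3)/(2n − 4). At n = 25 this is 47/46 = 1.022, giving 0.930, 0.766, 0.521, or net cuts of 7.0%, 23.4% and 47.9%.
- Change score: 2(1 − ρ) = 1.4, 1.0, 0.6.

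**Width of the 95% CI** at n = 25: √(net variance) × t(0.975, 47)/t(0.975, 48) = 0.965, 0.876, 0.722, so about 4%, 12% and 28% narrower.

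**Power for 0.5 SD** (noncentral t, noncentrality 0.5/√(2v/n), where v is the relative variance, net of the slope cost for ANCOVA):

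| n per arm | ρ | t test, week 12 | ANCOVA | t test on change |
|---|---|---|---|---|
| 10 | 0.3 | 18.5% | 18.9% | 14.6% |
| 10 | 0.5 | 18.5% | 21.9% | 18.5% |
| 10 | 0.7 | 18.5% | 30.0% | 27.7% |
| 25 | 0.3 | 41.0% | 43.5% | 31.0% |
| 25 | 0.5 | 41.0% | 50.7% | 41.0% |
| 25 | 0.7 | 41.0% | 67.0% | 60.9% |
| 50 | 0.3 | 70% | 73% | 55% |
| 50 | 0.5 | 70% | 81% | 70% |
| 50 | 0.7 | 70% | 93% | 89% |

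In simulation (40,000 trials per setting, normal on the log scale), Mann-Whitney on week-12 values has power of about 38.5% at n = 25. Type I error at ρ = 0.5 was 0.048 to 0.050 for ANCOVA.

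**Where the gain vanishes.** At ρ = 0 the factor is 1.010, 1.022 and 1.063 for n = 50, 25 and 10, so variance rises by 1%, 2% and 6%. Break-even is ρ = √(1 − 1/factor) = 0.10, 0.15 and 0.24. At n = 25, ANCOVA power is 41.6% at ρ = 0.2 and 40.6% at ρ = 0.1, against 41.0% unadjusted.

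**The case against.** **The comparator is not established.** A t or Mann-Whitney test on changes from baseline fits the SAP's wording and list, and would already use the pre-dose value. This stands as a description of the text: mentioning change only for metformin is weak evidence in so terse a plan. It does not defeat the point. Before the slope cost, the variance of ANCOVA relative to a change score is (1 − ρ²)/[2(1 − ρ)] = (1 + ρ)/2, that is 0.65, 0.75 and 0.85 at ρ = 0.3, 0.5 and 0.7. ANCOVA therefore wins on that reading too, and by most when the correlation is low. The caveat about low correlation applies only if week-12 values are compared.

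**The gain rests on assumptions and may be small.** This also stands. Sampling was not standardised: "The blood samples were taken randomly (no hours or gaps between metformin taking were defined". The pre-dose sample is also off drug, before the run-in and 12 weeks before the outcome. All this could lower the correlation.

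**An unadjusted comparison of randomised groups is valid.** True, and no error of validity is alleged. The case is that a better method is available from data already collected.

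**A figure in the SAP section is not shown, and the F test is unexplained.** Both limit certainty, so the point is confined to the readable text.

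**The remedy goes beyond adjustment.** Analysis by randomised group, the log scale and week 12 do not follow from the precision argument; they are needed to define the comparison. Analysing as randomised may also change the size of the effect. The power figures hold it at 0.5 SD, so they show the contribution of ANCOVA alone.

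**Conclusion.** The concern holds, as a change that should be made rather than a flaw that invalidates the comparison. The readable SAP names no baseline-adjusted A versus B analysis, while a valid covariate was collected for every compound. The trade is uneven: at 25 per arm, ANCOVA costs about 2% in variance if the correlation is zero, and saves about 23% at a correlation of 0.5. At correlations of 0.1 to 0.2, or at 10 per arm with 0.3, it makes almost no difference to power. Confidence in the size is medium, because correlation, sample size, effect and distribution are all assumed.

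**What to change.** For each compound, compare week-12 log concentration between groups as randomised, using ANCOVA adjusted for the pre-first-dose log concentration. For this analysis, keep group B patients who step down under Methods item 7 in group B. Report the ratio of geometric means with its 95% CI, and the number in each group without a week-12 value, including those excluded under item 8.

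Week 12 is the natural time for the contrast, since "after 12 weeks this group returned to the dose 3 x 500 mg for the next 3 weeks", so by week 15 both groups are on the same dose. The log scale is a choice, as the documents give no distributions.

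The week-6 value could serve as a covariate only if it precedes randomisation. Methods item 6 places randomisation after 3 weeks, and the flow chart places it after a control visit. These must be reconciled first. The pre-dose value is safe either way.

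**Cost.** No new samples; one degree of freedom; and a variance increase of about 1% to 6% (50 down to 10 per arm) if the correlation is near zero. Recruitment ended in December 2018 and the SAP is in the past tense, so this is probably a short re-analysis of existing data, to be labelled as such if results have been seen. If the analysis has not been run, only SAP wording changes.
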